#### CONFIDENTIAL

This material is the property of the NYU School of Medicine and Langone Medical Center. Do not disclose or use except as authorized in writing by the study sponsor

Use of continuous glucose monitoring system with intensive feedback in adolescents with poorly controlled type 1 diabetes  
Version Date: 04/26/2018

Dichotomizing participants into adherent and non-adherent:

Study subjects will receive points for calibrating the CGM device and for successfully completing phone contact with the pediatric diabetes team. The patient will receive 2 points for calibrating the device 2 times/day for at least 5 days, 1 point for calibrating the device 2 times on at least 3 days and 0 points for calibrating any less. Similarly the patient will receive 2 points for completing successful phone contact with study personnel for at least 5 days, 1 point for completing phone contact on at least 3 days and 0 point for contact any less than mentioned before. The two scores will be added to get a total score. Patients with scores 3-4 will be classified as adherent and scores 0-2 will be classified as non-adherent. Control subjects who complete 4 or more phone calls on different days will be classified as adherent and those who complete fewer phone calls will be classified as non-adherent.

Statistical methods:

Demographic data will be tabulated. Statistical analysis of questionnaires will be done according to published standards. The paired t-test will be used for comparisons involving stages of change score.

Independent variables will include the empowerment score, average glucoses, HbA1c and whether the subjects fall into the adherent vs. non-adherent groups. Dependent variables include glucose level(s) and stage of change. We will analyze the 7 day average glucose by meter download and categorize the results in terms of change: No change (-15 to + 15), Higher ( $\geq + 15$ ) or Lower ( $\leq -15$ ). We will analyze the HbA1c and categorize the results in terms of change: No change ( $> -0.5$  to  $+ 0.5$ ), Higher ( $\geq + 0.5$ ) or Lower ( $\leq -0.5$ ). Stages of change (Appendix A) will be categorized as unchanged, improved or worsened. In addition, descriptive statistics including quality of life, diabetes knowledge scale, and demographic variables will be tabulated.

Statistical Analysis for sensor study:

Questionnaires:

Demographics (Appendix G): data will be put in table form, with range, mean, s.d. scores for age; % Male/Female; and descriptive data for the remainder of the items. In Questions #11, 13 and 14, with 1-5 scales, the range, mean, and s.d. scores will be given. Stages of Change (Appendix A): scores can be given categorically, with each question assigned a score of 1 for a “yes” answer, and zero for a “no” answer; then range, mean, s.d. will be calculated before and after the intervention. In addition, a “yes” or “no” answer to these questions will determine which “stage of change” category the subject belongs in, according to the definition of “stages of change”. This is categorical data. We will analyze movement in the “stages of change” by comparing the score before and after the study intervention. This will be categorical: improvement, no change, deterioration.

CONFIDENTIAL

This material is the property of the NYU School of Medicine and Langone Medical Center. Do not disclose or use except as authorized in writing by the study sponsor

Use of continuous glucose monitoring system with intensive feedback in adolescents with poorly controlled type 1 diabetes  
Version Date: 04/26/2018

Diabetes Empowerment Scale-Short Form (Appendix B): the average of the scores of the completed items will be tabulated. Each question is answered as 1-5, and there are 8 questions. Thus, the scores can range from 1-5. The scores will be compared before and after study intervention.

Diabetes Knowledge Test (Appendix C): There are 23 multiple choice questions, scored as correct or incorrect. This will be administered only at baseline.

Peds Quality of Life 3.2 Diabetes Module: (Appendix D): There are 33 questions with Likert scale answers (0-4). Scores are transformed on a scale of 0-100. This test will be administered before and after the study intervention.

PHQ-2: (Appendix E): The score ranges from 0-6. The scores will be compared before and after the study intervention.

CGM Satisfaction Scale: (Appendix F): We are using an abbreviated version of a previously published CGM-SAT scale. Each question is scored 1-5 and the mean is calculated. This will be given after the intervention and only in the intervention group.

Daily Phone Log: (Appendix H): Scoring will be done for each day of the initial week of the study, in both CGM intervention group, and control group based on the following: Study subjects will receive points for calibrating the CGM device and for successfully completing phone contact with the pediatric diabetes team. The patient will receive 2 points for calibrating the device 2 times/day for at least 5 days, 1 point for calibrating the device 2 times on at least 3 days and 0 points for calibrating any less. Similarly the patient will receive 2 points for completing successful phone contact with study personnel for at least 5 days, 1 point for completing phone contact on at least 3 days and 0 point for contact any less than mentioned before. The two scores will be added to get a total score. Patients with scores 3-4 will be classified as adherent and scores 0-2 will be classified as non-adherent. Control subjects who complete 4 or more phone calls on different days will be classified as adherent and those who complete fewer phone calls will be classified as non-adherent.

The distribution of the data will be assessed using the Kolmogorov-Smirnov test. All categorical variables will be presented as mean +standard deviation. For categorical variables the differences between the compliant and non-compliant groups will be assessed using the Mann Whitney or rank order Wilcoxon test based on normality. For categorical variables independent sample t test will be used. Univariate analysis will be used to establish correlation between variables of interest.

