#### SUBJECTS:

Sixty adolescents, ages 13-22 years, with type 1 diabetes and an HbA1c  $\geq 8\%$  who are also naive to CGMS or who have not used a CGMS in at least six months use will be recruited from the diabetes outpatient population followed at Bellevue Hospital, Lutheran Hospital, Woodhull Hospital, and the NYU Fink Pediatric Ambulatory Care Center. Forty subjects will be randomly assigned to the CGMS group and 20 subjects will be assigned to the control group.

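### The 0-4 adherence score is split at 3 without a stated reason and only the two-group version is named for analysis; the information lost depends on a score distribution the plan does not give

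*Combined protocol and SAP*

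**What the plan says.** The rule is in the ANALYSIS section, under the subheading on dichotomizing participants, and is repeated under Daily Phone Log (Appendix H). A CGMS participant earns "2 points for calibrating the device 2 times/day for at least 5 days", 1 point for at least 3 such days and 0 otherwise. Phone contact is scored the same way: "2 points for completing successful phone contact with study personnel for at least 5 days", 1 point for at least 3 days, 0 for fewer. Then "The two scores will be added to get a total score", and "Patients with scores 3-4 will be classified as adherent and scores 0-2 will be classified as non-adherent". Controls have no 0-4 score; they count as adherent with 4 or more calls on different days.

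Statistical methods lists among the independent variables "whether the subjects fall into the adherent vs. non-adherent groups". The closing paragraph on tests says that "differences between the compliant and non-compliant groups will be assessed". No analysis of the uncut score or of the day counts is named, and no reason for the cut point is given.

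On size, the SUBJECTS section states: "Forty subjects will be randomly assigned to the CGMS group and 20 subjects will be assigned to the control group". The plan has no power calculation, significance level, effect size or expected distribution of the score.

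**The concern.** Adherence is one of four independent variables the plan names, and both arms are to be classified by it. Its relation to glucose and stage of change will be examined in at most 40 CGMS and 20 control participants. The information is reduced twice: day counts become 0, 1 or 2 points, and the summed points become two groups. Participants with very different behaviour end up in one class, and the result depends on a cut that is not argued for. At stake is avoidable loss of power in a named analysis, when the uncut quantities are already in hand.

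**Working it through.** The plan offers no figure to reproduce, so the check starts from its scoring rule.

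**Inputs from the documents.** 40 CGMS and 20 control participants (SUBJECTS); the scoring rule and cut (ANALYSIS); scoring over the initial week, so 0-7 days per task (Daily Phone Log).

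**Assumed.** The score distribution; an outcome linear in adherence; two-sided 5% significance.

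**Step 1: what the rule does to individuals.** This needs no assumption.

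| Calibration days | Call days | Task-days (of 14) | Points | Class |
|---|---|---|---|---|
| 0 | 0 | 0 | 0+0=0 | non-adherent |
| 7 | 2 | 9 | 2+0=2 | non-adherent |
| 4 | 4 | 8 | 1+1=2 | non-adherent |
| 5 | 3 | 8 | 2+1=3 | adherent |

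The participant with 9 task-days is classed below one with 8. Two participants with 8 fall on opposite sides. The 9-day participant shares a class with one who did nothing.

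**Step 2: information kept relative to the score.** Let S be the score, D = 1 if S ≥ 3 and p = P(D=1). With an outcome linear in S, the share kept is

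corr(S,D)² = cov(S,D)² / [var(S) · p(1−p)].

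Uniform scores: mean 2, var(S) = 2, p = 0.4, p(1−p) = 0.24. E[SD] = (3+4) × 0.2 = 1.4, so cov = 1.4 − 2 × 0.4 = 0.6. Share kept = 0.36 / (2 × 0.24) = 0.75, a loss of 25%; effective n = 40 × 0.75 = 30.

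Other shapes, by the same formula:

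| Distribution over 0,1,2,3,4 | Loss | Effective n of 40 |
|---|---|---|
| Uniform | 25.0% | 30.0 |
| 1:2:3:2:1 | 33.3% | 26.7 |
| .35, .30, .20, .10, .05 | 40.9% | 23.6 |
| .05, .10, .20, .30, .35 | 25.5% | 29.8 |
| .02, .03, .05, .10, .80 | 19.9% | 32.0 |
| .30, .15, .10, .15, .30 | 15.8% | 33.7 |
| Strongly U-shaped | 7.7% | 36.9 |
| Only 0s and 4s | 0% | 40.0 |

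The percentage does not depend on the arm size, which sets only the effective n.

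**Step 3: a seven-day model.** Participants differ in a Beta-distributed daily completion probability with mean 40-80%, and days are binomial out of 7. The loss ranges from about 12% to 48% against the score and from about 19% to 64% against the summed day count. One strongly clustered propensity behind both tasks gives 12-22% against the score; independent tasks give 21-48%. For controls (means 50-80%, Beta precision 3), the cut at 4 calls keeps 63-74% of the information in call days.

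**Step 4: power, two assumed examples at n = 40.**

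(a) Fisher z: power ≈ Φ(atanh(r)·√37 − 1.96). With r = 0.43 against the score, atanh(0.43)·√37 = 2.80 and power is 80%. A 25% loss gives r = 0.43·√0.75 = 0.372 and 66%. A 40% loss gives r = 0.43·√0.60 = 0.333 and 56%.

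(b) Simulation: Beta propensities with precision 3 and correlation 0.5, mean completion 50%, 65% and 80%, and the latent propensity explaining 20% of outcome variance.

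| Form of adherence | Power |
|---|---|
| Adherent/non-adherent split | about 50-55% |
| 0-4 score | 64-71% |
| Sum of call and calibration days | 71-75% |
| Two counts as separate predictors, tested jointly | about 61-65% |

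Repeat runs at 80% completion put the split at 47-50%, so its lower end is accurate only to a few points.

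**The case against.** Several objections have weight.

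- **The size is not a property of the documents.** A reader might infer a fixed loss of a quarter to two-fifths of the score's information. The plan does not support that, because it gives no score distribution. If the same adolescents tend to do both tasks or neither, scores pile up at the ends and the loss falls to about 8-22%. Losses near two-fifths of the score need low or unrelated completion, or else belong to the comparison with day counts. This stands, and it is why a wide range is given.
- **A threshold could be real.** If outcomes changed only at a score of 3, the cut would lose nothing. That is possible, but the plan does not argue it.
- **The split is the only adherence variable defined in both arms.** Controls do not calibrate and have no 0-4 score. This stands as a real cost of replacing it in the CGMS arm, and the fix has to deal with it.
- **An uncut analysis is not excluded.** The list of independent variables is not closed, calls are tallied, and the last sentence on tests promises univariate correlations between unspecified variables. So one cannot say that the uncut score will never be analysed, only that no such analysis is named.
- **More detail is not always better.** Entering both day counts as separate predictors gives less power in the example than the single 0-4 score.
- **The examples use a continuous outcome.** The plan also puts changes in glucose, HbA1c and stage into three categories, to which these power figures do not carry over directly.

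A reader might also infer that the trial's glycaemic result is weakened. It is not: HbA1c at entry and 3 months is compared without using the split.

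**Conclusion.** The point holds as a cheap improvement. The cut is unexplained, can rank a participant who completed more below one who completed less, and costs information in the only adherence analysis the plan names. Assuming linearity, the loss is roughly 10-45% of the information in the 0-4 score over plausible distributions, and more against the day counts. It reaches zero only in the limiting case of scores at 0 and 4 alone. In the assumed example, moving from the split to a single ordered or numeric measure raises power by roughly 10 to 25 percentage points. All these figures rest on assumed distributions and effect sizes; the defect and its remedy do not. The effect is limited to the adherence analyses.

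**What to change.** In the CGMS arm, name one ordered or numeric adherence predictor: either the 0-4 score or the sum of call days and calibration days (0-14). Analyse it by rank correlation or regression. Do not enter the two counts as separate predictors for the main test. In controls, use the number of call days (0-7). For any analysis that pools the arms, use call days, which both arms have. Keep the adherent/non-adherent split for the descriptive table.

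The cost is a change of wording in the adherence rule, Statistical methods, the Daily Phone Log entry and the closing paragraph on tests. No new data are needed: calls are already tallied, and calibration days must be counted to apply the scoring rule. The downside is small: the CGMS measure is not on the same scale as the control measure, and a slope is reported in addition to two group means.

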
### AIM:

To determine if short-term use of continuous glucose monitoring systems (CGMS) with intensive real time feedback about diabetes management from medical staff to the patient will affect motivation and/or behavior, in adolescents with poorly controlled type 1

CONFIDENTIAL

This material is the property of the NYU School of Medicine and Langone Medical Center. Do not disclose or use except as authorized in writing by the study sponsor

Use of continuous glucose monitoring system with intensive feedback in adolescents with poorly controlled type 1 diabetes  
Version Date: 04/26/2018

diabetes. Previous CGMS studies have tended to focus on participants who are in better glycemic control at baseline and who report better adherence and diabetes-related quality of life than expected of a randomly selected sample of subjects with type 1 diabetes.

Studying a more broadly representative group that includes subjects with poor glycemic control will provide helpful information about glycemic and psychological effects of CGMS in an at risk group(1). Research indicates that various psychological skills and psychosocial factors, including coping and social support play a large role in the efficacy of CGMS use(2).

We hypothesize that short-term CGMS use with feedback (and/or lack thereof) and patients' sense of self-efficacy will influence their stage of change and potentially glucose levels.

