#### CONFIDENTIAL

This material is the property of the NYU School of Medicine and Langone Medical Center. Do not disclose or use except as authorized in writing by the study sponsor

Use of continuous glucose monitoring system with intensive feedback in adolescents with poorly controlled type 1 diabetes  
Version Date: 04/26/2018

appointments and staff will determine if they are interested in participation in the study using a recruitment script uploaded under recruitment materials section.

The study is minimal risk (MR). The device is approved by the FDA and is being used according to its cleared/approved labeling. The probability and magnitude of harm or discomfort anticipated in this research is similar to those ordinarily encountered in daily life or during the performance of routine physical or psychological examinations or tests.

The use of the CGMS will be described.

The study will consist of 4 phases.

1: For all participants at entry into the study the participant's HbA1c will be measured in the lab at the location of the patient's visit and his/her glucose meter will be downloaded as part of routine care. The average capillary glucose level, (with range and standard deviation) and the average number of tests per day over the prior 14 days will be recorded. The current individual care plans for self-management of type 1 diabetes will be reviewed by the study personnel with the participant.

Questionnaires will be administered to all the participants except Appendix F:

- 1) Appendix A - Stages of Change measure (original). We created a 5 item questionnaire to assess the patient's current stage.
- 2) Appendix B - Psychosocial self-efficacy (University of Michigan Diabetes Research and Training Diabetes Empowerment Scale short-form) - DES. 8 items. Also available for use.(3-6)
- 3) Appendix C - Knowledge and risk perception (University of Michigan Diabetes Research Training Center Diabetes Knowledge Scale). 23 items - DKT. We are substituting rapid acting insulin for NPH insulin in item 17 since NPH is not used in our study population. Available for use without permission as long as the source is quoted.(7, 8)
- 4) Appendix D - Quality of life (Peds QL 3.2, Diabetes module,) – Peds QL. 33 items on a Likert scale.(9)

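### The only test named for stage of change is a within-person paired t-test, so the plan has no CGMS-versus-control comparison for an outcome its hypothesis names

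*Combined protocol and SAP*

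**What the plan says.** The AIM section hypothesises that short-term CGMS use with feedback, or its absence, together with self-efficacy, "will influence their stage of change and potentially glucose levels". SUBJECTS randomises 40 participants to CGMS and assigns 20 to control. Both groups attend at 1 week, 1 month and 3 months, and the Stages of Change measure is given at entry and at each of these visits.

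The instrument is the investigators' own: "We created a 5 item questionnaire to assess the" participant's current stage. Under ANALYSIS, Statistical methods, stage of change is a dependent variable and the test is named: "The paired t-test will be used for comparisons involving stages of change score". The same paragraph adds: "Stages of change (Appendix A) will be categorized as unchanged, improved or worsened".

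The Stages of Change entry under Statistical Analysis for sensor study describes two quantities. One is an item score, "with each question assigned a score of 1 for a" yes and zero for a no; "then range, mean, s.d. will be calculated before and after the intervention". The other is a stage category determined by the answers. Movement between stages is then to be analysed "by comparing the score before and after the study intervention. This will be categorical: improvement, no change, deterioration". No test is attached to that three-way classification.

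**The concern.** The hypothesis concerns what CGMS with feedback does, and the trial randomises a control group to answer that. A within-person test leaves the control group out of the inference. Participants may change because they joined a study, were interviewed, answered questionnaires repeatedly, or were seen more often. The protocol also scores controls on completed phone calls during the first week, so some change in the control arm is plausible. A paired test cannot separate such change from an effect of the device and feedback.

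A smaller matter concerns the variable itself. If the score means a count of yes answers, the tested quantity need not be the stage that the hypothesis names.

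**Working it through.** **Is the arm contrast supplied anywhere else?**

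| Place in the plan | Contrast stated |
|---|---|
| ANALYSIS, opening paragraph | Questionnaire scores between visits (entry, 1 week, 1 month, 3 months) |
| Statistical methods, test for stage of change | Paired t-test, within person |
| Statistical methods, independent variables | Empowerment score, average glucose, HbA1c, adherence group; randomised arm is not listed |
| Statistical methods and sensor-study section, movement in stage | Three categories, no test and no grouping |
| Closing statistical paragraph, after the Daily Phone Log entry | Mann-Whitney or Wilcoxon for compliant versus non-compliant; an independent-sample t-test with no grouping given |

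None of these compares CGMS with control on stage of change. No matching of participants across arms is described, and 40 against 20 could not be paired one to one, so the paired test cannot be a between-arm test.

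**What could a significant paired test mean?** The plan has no figure to reproduce: it gives 60 participants (40 and 20) but no alpha, power, SD or effect size. The following is therefore an illustration. Assume two-sided alpha 0.05, complete data, and the same true standardised change d (mean change divided by SD of change) in both arms, so the true arm effect is zero. Power of a paired t-test comes from the noncentral t distribution with n − 1 degrees of freedom and noncentrality d√n. At d = 0.5 the noncentralities are 0.5√40 = 3.16, 0.5√20 = 2.24 and 0.5√60 = 3.87. The plan does not say whether the test is run by arm or on everyone, so both are shown.

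| d in both arms | CGMS, n = 40 | Control, n = 20 | Pooled, n = 60 | CGMS significant, control not | Control significant, CGMS not |
|---|---|---|---|---|---|
| 0.2 | 23.5% | 13.6% | 33.2% | 20.3% | 10.4% |
| 0.4 | 69.4% | 39.7% | 86.2% | 41.8% | 12.1% |
| 0.5 | 86.9% | 56.5% | 96.8% | 37.9% | 7.4% |

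The fifth column is the product of the CGMS probability and one minus the control probability; at d = 0.2 it is 0.235 × (1 − 0.136) = 0.203. The imbalance between the last two columns comes from the 2:1 allocation, because the larger arm is more likely to reach significance for the same change.

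A simulation of a 0–5 score with identical change in both arms (20,000 runs) gave CGMS significant and control not in 41.4%. A direct between-arm t-test on change was significant in 4.99%.

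**What can a between-arm test detect?** For a two-sample t-test on change, the noncentrality is d / √(1/40 + 1/20) = d / 0.274 with 58 degrees of freedom, where d is now the difference between arms in SDs of change. Power is 19% at 0.3, about 43% at 0.5 and 80% at 0.78. A rank or ordinal analysis would differ somewhat.

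**Score or stage?** Five items at 1 or 0 would total 0 to 5 if summed, although summing is not stated. If the items are strictly cumulative, the total ranks people as the stage does. If they are mutually exclusive stage statements and each participant endorses exactly one, every total is 1 and there is nothing to test. Appendix A is not in the supplied text, so the trial cannot be placed between these ends.

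**The case against.** Four things can be said for the plan.

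First, a reader might infer that the assigned stage is ignored. The documents do not support that. A stage is assigned to each participant, and movement is classified as improved, unchanged or worsened. What is missing is a test for that variable and a comparison of arms.

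Second, a reader might infer that the outcome will be misclassified because a sum replaces the stage. That is not shown either. In the sensor-study section the word score follows directly after the sentences that assign the stage category, and may simply mean the stage. Only the ambiguity stands.

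Third, the closing statistical paragraph mentions an independent-sample t-test without a grouping, which might have been meant for CGMS versus control. The only groups named in that paragraph are compliant and non-compliant, and the sentence names neither stage of change nor a visit. It does not fill the gap.

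Fourth, the missing arm comparison is not peculiar to this scale. The glucose, HbA1c and DES comparisons are also stated between visits. That is correct. It widens the problem and does not excuse it here, but this point may be merged with a plan-wide one.

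The percentages above are also not this trial's error rates. They rest on assumed effect sizes, and the columns by arm assume separate tests that the plan does not specify.

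**Conclusion.** The point holds for the missing comparison. As written, the plan never uses the randomisation to test stage of change, and the one test it names would credit change over time to CGMS with feedback. This follows from the text and does not depend on Appendix A or on any assumed figure.

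The size is illustrative only. With no arm effect and an equal change of 0.2 to 0.5 SD in both arms, a pooled paired test is significant in 33% to 97% of trials. Separate tests give the misleading pattern of CGMS significant and control not in about 20% to 42%.

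The question of score against stage is a secondary defect of wording. Its consequence, if any, depends on Appendix A. Nor should stage of change be read as the trial's sole or primary outcome: the hypothesis also names glucose levels, and no single primary endpoint is declared.

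**What to change.** Change the analysis text as follows.

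- Make the inferential analysis a CGMS-versus-control comparison of change in the assigned, ordered stage. A rank-sum test on change in stage, or a proportional-odds model adjusted for baseline stage, would serve.
- Name one lead visit from 1 week, 1 month and 3 months, and treat the other two as supportive, so that three tests are not run without a rule.
- Define improved, unchanged and worsened by the assigned stage. State how a stage is assigned when the answers do not fit a single one.
- Keep the item score and the within-arm paired t-test as descriptive.

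The data are already collected in both arms, so the cost is wording only. Two limits should be acknowledged. With 20 controls, sparse stages may have to be merged, and the merging rule should be set before the data are seen. Power is also limited, at roughly 80% for a difference of 0.78 SD of change under the assumptions above, so a non-significant result should be reported with its confidence interval and not read as no effect. The same change is needed for the other outcomes and could be made once for the whole plan.

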#### Exclusion Criteria:

Patients with developmental delay, and patients who do not use a glucose meter to test capillary blood glucose level, and patients without access to a telephone will be excluded.

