#### ANALYSIS:

Measures of the level of glycemic control will be assessed primarily by HbA1c and secondarily by the average glucose tests results on the patient's glucose meter. Comparison of the glucose results (average, range, standard deviation, number of daily tests) between the study entry, 1 week, 1 month and 3 month follow up visits will be done. Comparison of HbA1c at entry and at 3-month follow-up will be performed. Questionnaire scores will be compared between study entry, 1 week follow up, 1 month follow up and 3-month follow-up visits for DES and Stages of Change scales. We will determine if there is a correlation between the scores on the questionnaires and measures of glucose control. We will classify study and control participants into adherent and non-adherent groups.

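### The stages-of-change score is tested by paired t-tests with no rule for missed visits, so the 3-month change describes attenders and may be biased in either direction

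*Combined protocol and SAP*

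**What the plan says.** Under METHODS (phases 1 to 4), the Stages of Change form and the DES short form are given to both arms at entry, 1 week, 1 month and 3 months. The ANALYSIS section plans comparisons across entry, 1 week, "1 month follow up and 3-month follow-up visits for DES and Stages of Change scales".

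- **Stages of change.** Statistical methods states: "The paired t-test will be used for comparisons involving stages of change score". It does not say which visits are paired, or whether the test is run within an arm or on both arms together. A categorical version is also planned: "Stages of change (Appendix A) will be categorized as unchanged, improved or worsened". It too needs both measurements.
- **DES.** The questionnaire section says only: "The scores will be compared before and after study intervention". No test is named.
- **Sample.** SUBJECTS gives 60 in total: "Forty subjects will be randomly assigned to the CGMS group and 20 subjects will be assigned to the control group".
- **Missing data.** The only text is the Case Report Forms rule that missing entries be explained. That is a data-recording rule. The plan has no expected dropout, analysis population, repeated-measures model, imputation rule or sensitivity analysis.

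**The concern.** The aim is the effect on motivation and/or behavior in adolescents with poorly controlled diabetes. In such a trial, turning up for follow-up is plausibly related to the outcome itself. The plan gives grounds to expect uneven engagement. The background describes adolescents as often resistant to wearing the device and cites inconsistent use. The analysis sorts participants into adherent and non-adherent. The device goes back at 1 week, and the visit payment falls from $50 at 1 week to $20 at 1 and 3 months.

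A paired test discards what is known about a participant who lacks the second visit. The entry-to-3-month result then estimates the change in those who attended at 3 months, not in those enrolled. The comparisons at 1 week, 1 month and 3 months can each rest on a different set of people, so a trend across them mixes change over time with change in who is counted. If attendance differs by arm, the same problem carries into any CGMS-versus-control comparison built on these changes.

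**Working it through.** The plan states no effect size, SD, correlation or dropout, so there is no planned figure to reproduce. From the documents: 40 + 20 = 60 participants and four visits. Everything else below is assumed.

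**1. Who remains.** If 10%, 20% or 30% miss the 3-month visit, the entry-to-3-month test keeps 60 × 0.9 = 54, 60 × 0.8 = 48 or 60 × 0.7 = 42. At 30% the arms hold 28 and 14.

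**2. Bias of the paired estimate.** Let m be the share missing at 3 months, and G the mean change in attenders minus that in non-attenders. The mean over everyone is (1 − m) × attenders + m × non-attenders, so

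bias = attenders − everyone = m × G.

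With m = 0.20 and G = +0.5 SD the bias is +0.10 SD; with G = −0.5 it is −0.10. With m = 0.30 it is ±0.15. The sign is that of G, which the documents do not give.

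**3. Why G can take either sign.** Put scores in SD units with entry mean 0, true change 0.5, and correlation r between entry and 3 months. The expected change for someone with entry score y is

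0.5 − (1 − r) × y.

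With r = 0.5, a person 1 SD below the mean at entry is expected to change by 0.5 + 0.5 = 1.0, and a person 1 SD above by 0.5 − 0.5 = 0. If those with low entry scores leave, attenders show too little change. If those who had improved little by 1 month leave, attenders show too much.

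**4. Simulation, true change 0.5 SD.** Means were 0, 0.5, 0.5, 0.5 with unit SD. Correlation was 0.5 or 0.7, either constant or decaying with each visit. Only the 3-month visit was missing, at 20–30% overall, with log-odds slope 0.5 or 1 per SD of the driver (odds ratios e^0.5 = 1.65 and e^1 = 2.7). There were at least 100,000 simulated participants per setting. The all-visits estimate uses the entry, 1-week and 1-month scores to supply the expected 3-month score of those who missed it.

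| Who leaves | Paired estimate | All-visits estimate |
|---|---|---|
| Little change at 1 month | 0.54–0.73 | about 0.50 |
| Low entry score | 0.28–0.47 | about 0.50 |
| Little 3-month change (unseen) | 0.57–0.84 | 0.55–0.67 |

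Against 0.50, the first row is 0.04/0.50 = 8% to 0.23/0.50 = 46% too high. The second is 0.03/0.50 = 6% to 0.22/0.50 = 44% too low. The extremes, 0.73 and 0.28, come from decaying correlation, where the entry-to-3-month correlation can be as low as 0.5³ = 0.125. With constant correlation the upward case reaches about 0.62, or 24%.

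**5. Second simulation, true change 0.30 SD.** Correlation was constant at 0.6, with about 22–32% missing where the loss depends on scores. For completely random loss the shares were 18% and 29%.

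| Who leaves | Paired | All visits |
|---|---|---|
| Completely at random | 0.30 | 0.30 |
| Low score at 1 month | 0.30 | 0.30 |
| Little change at 1 month | 0.38–0.41 | 0.30 |
| Large change at 1 month | 0.19–0.22 | 0.30 |
| Low entry score | 0.19–0.22 | 0.30 |
| Little 3-month change (unseen) | 0.45–0.52 | 0.40–0.45 |
| Large 3-month change (unseen) | 0.08–0.15 | 0.15–0.20 |

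**The case against.** The strongest objection is that no passage gives an attrition rate or mechanism. The bias may be zero, as it is with random loss or, under constant correlation, with loss driven by the 1-month score. This stands, and it limits the point to a risk of bias with no predicted direction. A reader might infer that the planned test overstates the change because the unmotivated stop coming. The documents do not support that: loss of those with low entry motivation, which is equally plausible, makes the paired estimate too small.

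Three further limits also stand.

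- A reader might infer that the test drops everyone who misses any visit. The loss is per pair: someone who misses 1 week or 1 month still enters the entry-to-3-month comparison.
- A reader might infer that DES is also analysed by paired tests. The paired t-test is named for stages of change only, and for DES the analysis is unspecified.
- A repeated-measures model does not cure every case. When loss depends on the unseen 3-month change, it is biased as well, though less so. The simulations used normal scores in very large samples, so they do not show that an ordinal model can be fitted with 40 and 20 participants.

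It can also be said that the larger weakness is that a within-person test makes no use of the randomised control arm. The group comparison that the plan does name, at the end of the ANALYSIS section, is between compliant and non-compliant participants. That is fair. It supports the same repair, since the arm-by-visit term provides the missing arm comparison.

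**Conclusion.** The point holds in limited form. The only test named for the stages-of-change score uses complete pairs, and nothing in the plan uses the intermediate answers of those who miss 3 months. The 3-month change therefore applies to attenders.

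Under the assumed inputs (true change 0.5 SD, 20–30% missing at 3 months, loss related to observed scores), the error could be about +0.04 to +0.23 SD or about −0.03 to −0.22 SD, depending on who leaves. An all-visits estimate avoids both errors as long as the observed scores explain the loss. If they do not, it lessens the bias without removing it. The documents support neither a claim that the result will be inflated nor any single figure for the bias. The change is worth making because it uses data already being collected and works whichever way the bias runs.

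**What to change.** In Statistical methods, replace the paired t-test for the stages-of-change score with one repeated-measures model using all available visits:

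- **Model.** A linear mixed model for the 1-week, 1-month and 3-month scores with arm, visit, arm by visit and entry score, and an unstructured covariance. Letting the entry-score effect differ by visit matches the all-visits estimate in the working.
- **Estimates.** Read the 3-month change and the CGMS-versus-control difference at 3 months from the model, evaluated at the mean entry score of all randomised participants.
- **Stage category.** Use an ordinal version of the model if it can be fitted with 40 versus 20 participants. State the fallback in advance.
- **DES.** Name the same linear model, since no test is given now.
- **Attendance.** Report it by arm and visit, and compare entry scores of attenders and non-attenders at 3 months.
- **Sensitivity analysis.** Add one for missingness that depends on unseen values, for example by shifting the predicted 3-month scores of non-attenders over a stated range in each arm.

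The cost is SAP wording and slightly more analysis work. No new data are needed. The main model rests on the assumption that missingness is explained by observed scores, which is why the sensitivity analysis belongs with it.
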